8.3 Adverse Events and Serious Adverse Events

- **An adverse event (AE)** is generally defined as any unfavorable and unintended diagnosis, symptom, sign (including an abnormal laboratory finding), syndrome or disease which either occurs during the study, having been absent at baseline, or if present at baseline, appears to worsen. Adverse events have to be recorded regardless of their relationship to the study intervention.

- **A serious adverse event (SAE)** is generally defined as any untoward medical occurrence that results in death or that is life threatening, requires inpatient hospitalization or prolongation of existing hospitalization, results in persistent or significant disability/incapacity, or in a congenital anomaly.

As discussed in 8.1, the study solution is not a novel pharmaceutical product and is unlikely to cause any significant adverse event. Theoretical complications of the solution are common problems in critical care units. Vigilance and close monitoring, together with high staffing levels in ICU reduce the potential for harm. Bearing these facts in mind, there are only three scenarios, which will be reported as serious adverse events in the EMR group:

- 1) **Anaphylaxis (to study components)**
- 2) **Arrhythmia secondary to electrolyte disturbance**
- 3) **Hypoglycemia (<70mg/dL)**

These will be monitored for via electronic medical records. All suspected adverse reactions and above adverse events must be reported by unit staff or research team to the principle investigator who will provide within 1 week such reports to the Institutional Review Board. We estimate that adverse reactions are not very likely, as this study lacks novel pharmaceutical agents. Patient safety has been thoroughly considered by the study chairs.

Only the adverse events and serious adverse events that happen within the 7 days of enrollment will be logged and reported to the IRB.

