1.0 STUDY OBJECTIVES

1.1 Primary Objective:

To assess the efficacy of administering Early Metabolic Resuscitation with Standard of Care (SC + EMR) in patients diagnosed with septic shock for reducing 28-day mortality versus using the Standard of Care alone (SC). Twenty-eight day mortality is defined during the time from the day SC+EMR or SC was first administered until a patient dies or is followed through 28 days (whichever comes first).

1.2 Secondary Objectives:

1. To assess whether Early Metabolic Resuscitation with standard of care (SC + EMR) is an effective strategy to reduce ICU mortality, hospital mortality, and 90-day mortality of septic shock patients relative to SC. ICU mortality is defined as mortality at ICU discharge relative to SC.
2. To compare the time to death from any cause between patients administered SC + EMR versus SC after being diagnosed with septic shock.
3. To assess whether SC + EMR is an effective strategy to reduce complications of septic shock such as: i) acute kidney injury, ii) dialysis requirements, iii) need for cardiovascular support or days on vasopressors, iv) need for invasive ventilation, days on ventilator support, v) duration of ICU stay, and vi) duration of hospital stay versus SC.
4. To describe the presence of any adverse effects between the two study groups (SC + EMR group vs SC group); thus, characterizing their safety.

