- i. Study intervention is to be stopped. Record as adverse event. Manage as per ICU protocol

f. Hypomagnesemia (Mg <1.5mg/dl)

- i. Replace as per ICU guidelines – N.B. target magnesium is ≥ 3 mg/dl in intervention group

g. Aluminum toxicity

- i. Aluminum toxicity is seen in neonates; however, this population is excluded in our study.

- ii. Patients in renal failure are at risk of bio-accumulating aluminum when solutions contain >50 micrograms/L. In this study, patients with renal failure are excluded and free amino acids only contains <25 micrograms/L.
- iii. Currently, to measure blood aluminum levels is not standard of care in a) patients not at risk of bio-cumulating the metal, b) patients receiving solutions that contain aluminum below 50 micrograms/L.
- iv. Aluminum toxicity is not an expected adverse event in this study patient population.

h. Hypophosphatemia (PO4 <1mg/dl)

- i. Additional replacement as per standard ICU guidelines

i. Hyperphosphatemia (PO4 >6.5mg/dL)

- i. Check renal function and calcium. Discuss with principal investigator. Hyperphosphatemia is not usually symptomatic and does not usually cause direct toxicity. The product of calcium x phosphate should be less or equal to 60. Record as adverse event

3. Hyper/hypoglycemia (see appendix)

For the very likely event of hyper/hypoglycemia in the EMR group we have developed an algorithm, which is a slight modification of standard ICU glucose management protocols and itself refers to ICU sliding scale insulin protocols. As glucose management is anticipated as a potential issue, monitoring of glucose is to occur at least hourly in the treatment arm. Please see appendix for detailed information on glucose management. Target glucose is 140-180mg/dl.

4. Allergic reactions (related to study components or suspected relation)

- Urticarial reaction
 - Begin antihistamine. Record as possible adverse event. Monitor patient – if EMR components suspected as the causative AND worsening reaction consider stopping solution and replace with D50 IV solution and exclude the patient from the protocol. At the same time treat the patient until reaction resolves. (Frequent glucose monitoring once solution discontinued). Contact principal investigator and follow hypersensitivity institutional protocol.
- Anaphylaxis

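### Section 8.3 states its SAE reporting list for the EMR group only, so SAE counts may not be comparable between arms, in either direction; glucose-event counts may also partly reflect unequal sampling

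*Combined protocol and SAP*

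**What the plan says.** Secondary objective 4 (section 1.2) is "To describe the presence of any adverse effects between the two study groups (SC + EMR group vs SC group); thus, characterizing their safety". Section 8.1 expects the main harms, including electrolyte disturbance and abnormal glucose, to be possible in either group.

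Section 8.3 opens with definitions that name no arm. An AE includes any "symptom, sign (including an abnormal laboratory finding), syndrome or disease" that is new or worse, and "Adverse events have to be recorded regardless of their relationship to the study intervention". An SAE is "any untoward medical occurrence that results in death or that is life threatening", or that meets one of the other usual criteria. The logging window also names no arm: "Only the adverse events and serious adverse events that happen within the 7 days of enrollment will be logged".

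Between these passages comes a narrower rule: "there are only three scenarios, which will be reported as serious adverse events in the EMR group". The three are anaphylaxis to study components, arrhythmia caused by electrolyte disturbance, and "Hypoglycemia (<70mg/dL". Nothing corresponding is said for SC.

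On glucose, section 8.2 says that "monitoring of glucose is to occur at least hourly in the treatment arm". Section 6.1 refers SC to the institutional septic shock algorithm and gives no glucose frequency. The only stated glucose schedule that names no arm is the chemistry panel in section 7.2: every 4 hours for the first 24 hours, then every 8 hours. Section 7.2 calls this a minimum and adds that further tests may go unrecorded.

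**The concern.** A between-arm description of safety needs the same event definition and comparable ascertainment in both arms. Section 8.3, as written, departs from the first for SAEs. Section 8.2 may depart from the second for glucose.

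At stake is the reading of the safety table. Section 8.2 itself treats abnormal glucose in the EMR group as very likely, so readers will look for it. An SAE table built on the stated rules could show an excess or a deficit in EMR that comes from the rule and not from the treatment. A glucose table could show an excess that comes partly from more frequent looking.

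**Working it through.** **Step 1. Classify the same event in each arm.** No figure in the plan needs reproducing here; the check is to apply the wording of 8.3. Two readings of its silence on SC are possible: (A) SC follows the general SAE definition; (B) SC has no SAE reporting.

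| Event within 7 days of enrollment | EMR | SC, reading A | SC, reading B |
|---|---|---|---|
| Glucose 65 mg/dL, no further consequence | SAE | AE only | AE only |
| Electrolyte-related arrhythmia, no general criterion met | SAE | AE only | AE only |
| Fatal or life-threatening event not on the list | Not a reported SAE | SAE | Not a reported SAE |
| Anaphylaxis to study components | SAE | Cannot occur | Cannot occur |

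Under A, the first two rows raise the EMR count relative to SC and the third raises the SC count relative to EMR, so the net direction is unknown. Under B there is no SC count to compare. Neither reading gives a like-for-like comparison.

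**Step 2. Check whether AE recording has the same fault.** The AE definition, the duty to record and the 7-day window name no arm. A low glucose found in an SC patient is therefore an AE to be recorded. There is one arm-specific trigger in 8.2: a potassium of 5.5 mmol/L or more is flagged for AE recording when EMR I is running, a condition that SC cannot meet, although the general AE definition still applies there.

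**Step 3. Count scheduled glucose readings over 7 days.**
- EMR, hourly for all 7 days (8.2): 24 × 7 = 168.
- EMR, hourly for 3 days (assumed early stop) and then the panel: 24 × 3 + 3 × 4 = 84.
- Panel minimum (7.2): 24/4 + 6 × (24/8) = 6 + 18 = 24.
- Ratios to the panel: 168/24 = 7 and 84/24 = 3.5.

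**Step 4. See whether this fixes the size of any bias.** With readings every T hours, an episode of d hours with random onset is detected with chance min(1, d/T). On the panel, averaged over 7 days, this is [min(1, d/4) + 6 × min(1, d/8)]/7. The documents give no episode length d, so the values below are assumptions, as are equal true rates in the two arms.
- SC events known only from the panel, EMR hourly throughout: for d = 1 hour, panel detection is (0.25 + 0.75)/7 = 0.143, so the EMR:SC ratio of detected episodes is 1/0.143 = 7. For d = 8 hours it is 1.0.
- SC checked hourly and recorded: the ratio is 1.0 for any d.
- Only the 7.2 draws counted, with EMR episodes corrected within 1 hour (assumed): EMR detection is 0.143. If SC episodes last 4 hours, SC detection is (1 + 3)/7 = 0.571 and the ratio is 0.143/0.571 = 0.25.

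The result runs from well below 1 to 7 depending on inputs that the documents do not supply. The formulas also assume exact draw times. The ±120-minute window allows gaps of up to 4 + 4 = 8 hours on day 1 and 8 + 4 = 12 hours later. So the calculation shows possible directions only: all recorded events can overstate EMR hypoglycemia, and scheduled draws alone can understate it.

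**The case against.** The strongest reply is that the three-item list concerns reporting and not data capture. The sentences after it send reports to the principal investigator and the Institutional Review Board, while AE recording is set out separately for both arms. Objective 4 speaks of adverse effects in general, and section 10.5 calls for no SAE table by arm. Mortality, kidney injury, dialysis and new infections are collected as outcome data with no arm named. Much of this stands: most of objective 4 can be met from AE records, and deaths are not lost. It does not remove the point, because 8.3 never says that the list is for reporting only, nor which SAE definition would serve the comparison.

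On glucose, 8.2 describes the EMR algorithm as a slight modification of standard ICU protocols, so SC patients presumably have bedside checks too. That also stands, and it is why no size can be given.

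Three stronger readings are tempting and unsupported. A reader might infer that SC has no SAE rule at all; the general definition names no arm and may apply. A reader might infer that the rules can only make EMR look worse; the word restricting EMR to three scenarios also drops other serious events from its count. A reader might infer a sevenfold detection excess for hypoglycemia; that needs SC glucose to be known only from the panel, hourly EMR checks for all seven days and short episodes, none of which the documents establish.

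**Conclusion.** The SAE part follows from the text: on either reading A or reading B, SAE counts by arm are not comparable, and under A the error can go in either direction. It would fall away only if the sponsor confirmed that the list governs expedited reporting alone and that one definition applies to both arms.

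The glucose part is a possibility, not a finding of bias. Scheduled readings could differ by as much as 168 to 24, but the effect on event counts depends on SC bedside testing, its recording and episode length. It is nil if SC checks are hourly and recorded.

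Severity is minor. Only the descriptive safety comparison is touched. The mortality endpoints and the single-arm safety rule in section 10.6 are unaffected.

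**What to change.** - **Section 8.3:** apply one SAE definition and one reporting list to both arms over the same 7 days from enrollment, with anaphylaxis to study components tabulated separately. If the three-item list is meant for expedited reporting only, say so.
- **Section 8.2:** state that the laboratory thresholds used to define AEs are recorded in both arms.
- **Section 10.5:** report glucose events by arm in two ways: all recorded events, and events on the 7.2 scheduled draws. Time those draws from an origin that both arms share, such as randomization or enrollment, because 7.2 now counts from the start of the intervention and SC has no infusion start. Note beside the tables that the first count can overstate and the second can understate EMR hypoglycemia.

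Clinical monitoring, the mortality endpoints and the 10.6 boundaries stay as they are. The cost is wording in three sections, some extra event entry for SC patients and one additional table. No new tests are needed. Neither glucose table is free of bias alone, so both need to be shown.

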5.3 Study Enrollment Procedures

- A. Upon admission to the Emergency room or MICU, patients diagnosed with septic shock will be referred by the ICU attending to the designated study personnel who will then screen the patient for inclusion and exclusion criteria. The Basic Metabolic Panel (BMP) and patient medical chart history will be reviewed. If patient meets inclusion criteria (and no exclusion criteria) the patient's primary attending will be contacted for permission to enroll patient into the study. If the attending physician agrees, the patient (or if patient unable to consent, the patient's Legal Representative Power of Attorney or Next of Kin) will be approached.
- B. A discussion will be held with the next of kin and/or patient as appropriate to discuss the study procedures, possible adverse effects and research rationale. Informed consent will be mandatory and we will provide ample time to answer any questions or concerns about the protocol. A fully informed consent will be recorded in writing as per local guidance. It will be made clear to the participant and relatives that they are under no obligation to participate in the study and are free to withdraw

at any time, without giving a reason. Please see appendix for consenting material. If there is a possibility of pregnancy (defined as women <60 who have not been postmenopausal for at least one year or have not had a hysterectomy) then a serum or urine B-HCG test will be taken (with consent) prior to enrollment into the study. Refusal of pregnancy test will be considered grounds for exclusion.

The research coordinator will track all the potential candidates (patients meeting inclusion criteria) not included in the study in parallel due to logistical limitations (e.g. lack of research staff on weekends).

- C. Screening will be within 12 hours of patient being admitted to the ICU. Recruitment and initiation of study solution (where applicable) must occur both within twelve hours of the recorded onset of septic shock and admission to the MICU.

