6.2 Description of EMR protocol group

The combined EMR solution will be infused at a set rate (<12hours or > 12 hours) as the main metabolic resuscitation strategy. Additional volume may be required to achieve euvoolemia. This will be in the form of either albumin (if serum albumin < 3 as mentioned below) or crystalloids depending on the clinical situation and the serum sodium content.

The early metabolic support components include the following:

Table 2 show the components of the EMR solutions per liter

Table 2. EMR Solution

EMR SOLUTION WILL BE PREPARED IN A BAG WITH THE FOLLOWING COMPONENTS	
EMR I (with potassium)	EMR II * (without potassium)
Dextrose 50% with Potassium Phosphate 30 mmol	Dextrose 50% with Sodium Phosphate 30 mmol
Sodium Acetate 75 mEq	Sodium Acetate 55 mEq
Sodium Chloride 75 mEq	Sodium Chloride 55 mEq
Thiamine 500 mg	Thiamine 500 mg
Folic Acid 1 mg	Folic Acid 1 mg
Zinc Sulfate 5 mg	Zinc Sulfate 5 mg
Selenium 60 mcg	Selenium 60 mcg
Copper 1.2 mg	Copper 1.2 mg
Chromium 12 mcg	Chromium 12 mcg
Magnesium Sulfate 16 mEq	Magnesium Sulfate 16 mEq
Multivitamin for Injection 10 ml	Multivitamin for Injection 10 ml

Insulin 25 units (actrapid)	Insulin 25 units (actrapid)
SPECIFICATIONS OF THE TREATMENT AND ADJUVANTS	

A. EMR solutions: will be infused at 0.5 ml/kg/h by CVC. If serum glucose is greater than 180mg/dL-250mg/dL, EMR solution will be infused at 0.25 ml/kg/h. Prior to starting EMR infusion, a bolus of 500mg IV of thiamine should be administered to all patients on SC+EMR arm of treatment.
 
B. Clinisol 15% AA. Infusion rate (IV) will be 0.25 ml/kg/hr for the first 12 hours, then 0.5 ml/kg/h for the remainder of the intervention – this must be infused via a dedicated Central Venous Catheter.
 
C. If serum albumin is lower than 3 g/dL, then use Albumin 25% 100ml IV Q 8 hours until serum albumin level \geq 3 g/dL – this can be infused peripherally or centrally. Once albumin >3g/dL this can be stopped, but should resume whenever albumin falls <3g/dL
 
D. Vitamin C 1g q 8h IV (100 ml per gram of Vitamin C)
	

**If the level of K is \geq 5.0mmol/L the patient will receive EMR II. Any conditions, which the K⁺ trend is rising, clinicians could opt to switch EMR solution to prevent hyperkalemia.*

This solution does not contain potassium phosphate, but contains sodium phosphate. Sodium content is consequently adjusted to have a compatible concentration

Total amount of administered fluids on day one.

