6.3 Duration of intervention

The above infusions will be started and continued for seven days unless the patient dies or is discharged from the ICU. Infusions have to be continuously maintained and not stopped for any routine investigations. If the patient is tolerating enteral tube feeds at $\geq 70\%$ of goal for a full 24 hours as determined by the ICU dietician, the intervention will be stopped (established weaning process to avoid precipitation of hypoglycemia).

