6.7 Weaning procedure for EMR solution

To wean EMR, decrease rate of both solutions, EMR I or II and Clinisol to half the current rate for 4 hours, and then discontinue. Check serum glucose within 30 minutes of discontinuation of EMR. Further decisions regarding management of IVF, amino acid infusions or parenteral nutrition will be at the discretion of the ICU team or the primary team.

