10.6 Safety monitoring for Patients assigned to (SC + EMR)

Patient safety will be monitored group sequentially for the first 50 patients in (SC + EMR) group. The monitoring rule will be applied in cohorts of size 10 during the 7 days of treatment.

Patient safety will be monitored to ensure that the rate of select AEs described in Section 8.2 (which include: severe fluid overload, untreatable electrolyte abnormalities, severe hyper/hypoglycemia, allergic reactions) does not exceed 25%. If the AE rate exceeds 25%, then the novel treatment approach of (SC + EMR) exceeds an acceptable rate and the trial will suspend accrual, while at the same time, protecting patients from the burden of being exposed to an untoward therapy.

We will employ Bayesian stopping boundaries derived using a beta-binomial distribution. We will consider the treatment as acceptable if the AE rate during the first seven days post administration of (SC + EMR) is below 25%. The following prior probability for the AE rate will be modeled with a beta distribution (1, 1). Allowing θ_T to denote the true rate of AEs, the trial will suspend accrual if the $\text{Prob}(\theta_T > 0.25 | \text{data}) > 0.80$. Patients will be monitored in cohorts of size 10 according to the following stopping boundaries displayed in Table 3.

Table 4 illustrates the operating characteristics associated with the Bayesian stopping rule. The probability of stopping accrual early is 61% if the true AE rate is 30%.

Table 3. Stopping Boundaries assuming prior $\theta_T \sim \text{beta}(1, 1)$

Number of Patients Evaluated	Recommended stopping accrual if \geq AEs are observed
10	4-10
20	7-20
30	10-30
40	13-40
50	15-50

*stopping boundaries and operating characteristics supplied using

<https://ibl.mdanderson.org/BTM/>

Table 4: Operating Characteristics for the Bayesian Sequential Design

True AE Rate	Probability of Stopping Accrual Early	Average Sample Size
0.1	0.014	49.5
0.2	0.180	43.7
0.3	0.610	29.9
0.4	0.928	17.7
0.5	0.996	12.3

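### AE and SAE logging closes 7 days after enrollment, so in patients who complete or nearly complete the 7-day EMR course the post-stop glucose check, and possibly the wean, fall outside the log

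*Combined protocol and SAP*

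**What the plan says.** Four sections of the combined protocol and SAP set clocks that bear on this point.

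- **Logging (8.3):** "Only the adverse events and serious adverse events that happen within the 7 days of enrollment will be logged and reported to the IRB". The clock starts at enrollment. The same section lists hypoglycemia below 70 mg/dL as one of only three scenarios to be reported as SAEs in the EMR group.
- **Treatment (6.3):** "The above infusions will be started and continued for seven days unless the patient dies or is discharged from the ICU". The clock starts when the infusion starts.
- **Stopping (6.7):** the rate of both solutions is cut "to half the current rate for 4 hours, and then discontinue". Then: "Check serum glucose within 30 minutes of discontinuation of EMR".
- **Safety rule (10.6):** EMR is acceptable "if the AE rate during the first seven days post administration of (SC + EMR) is below 25" percent. The clock starts at administration.

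Section 5.3 bounds the interval between enrollment and infusion (the unit, cut off here, is the MICU) as follows: "Recruitment and initiation of study solution (where applicable) must occur both within twelve hours of the recorded onset of septic shock and admission to the". Section 6.2 places at least one step between allocation and infusion: "Prior to starting EMR infusion, a bolus of 500mg IV of thiamine should be administered". No section extends AE logging to the end of the infusion and wean.

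**The concern.** A seven-day log that opens at enrollment cannot fully cover a seven-day infusion that opens later and ends with a taper. The uncovered part is the period around stopping, which the protocol treats as needing care. Section 6.3 gives the purpose of the taper as "established weaning process to avoid precipitation of hypoglycemia", and 6.7 requires an early glucose check once the infusion is off. In a full-course patient the plan therefore requires a measurement whose abnormal result it does not require anyone to log or report.

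At stake is the fourth secondary objective, the description of adverse effects in the two groups. If a listed SAE occurs in the hours after a full course stops, it can be absent from the safety report even though the staff saw and treated it. Sections 8.3 and 10.6 also start their seven days at different moments, so the AE log and the safety rule need not count the same events.

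**Working it through.** **1. The plan's own figures.** Section 10.6 suspends accrual when Prob(AE rate > 0.25 | data) > 0.80 with a beta(1, 1) prior. After r events in n patients the posterior is beta(1 + r, 1 + n − r). The smallest r that crosses 0.80 is:

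| n | r | posterior probability at r | at r − 1 |
|---|---|---|---|
| 10 | 4 | 0.885 | 0.713 |
| 20 | 7 | 0.870 | 0.744 |
| 30 | 10 | 0.872 | 0.771 |
| 40 | 13 | 0.878 | 0.794 |
| 50 | 15 | 0.815 | 0.720 |

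These are the boundaries in the plan. An exact binomial recursion, counting stops at 10 to 40 patients, gives early-stop probabilities of 0.014, 0.180, 0.610, 0.928 and 0.996 at true rates of 0.1 to 0.5. The average sample sizes are 49.5, 43.7, 29.9, 17.7 and 12.3. All match. The rule is computed correctly; the question is which events reach it.

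**2. Inputs for the timing check.**
- Logging closes at 7 × 24 = 168 h from enrollment (8.3).
- The infusion lasts 168 h from its start (6.3).
- The wean takes 4 h, and the glucose check falls at most 0.5 h after stopping (6.7).
- The lag L from enrollment to infusion start is not given. I take enrollment to be the recruitment of 5.3. Recruitment and initiation share one 12-hour limit, so L is at most 12 h. The thiamine bolus puts it above zero. I use 0 to 12 h.

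**3. Full-course patient, hours from enrollment.** The documents do not say whether the wean is the last part of the seven days or follows them.

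| | Stop | Latest check | Check after closure |
|---|---|---|---|
| Wean inside: stop = L + 168 | 168 to 180 | 168.5 to 180.5 | 0.5 to 12.5 h |
| Wean after: stop = L + 168 + 4 | 172 to 184 | 172.5 to 184.5 | 4.5 to 16.5 h |

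If there were no wean at day 7, the stop and check would fall as in the first row.

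**4. How much of the wean is unlogged.** If the wean is inside, it runs from L + 164 to L + 168, so min(L, 4) hours of it fall after closure: none at L = 0, all 4 h once L reaches 4 h. If it follows, it runs from L + 168 to L + 172, and all of it is outside.

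**5. Who counts as nearly complete.** A patient stopped after T hours at full rate has the check inside the log if L + T + 4 + 0.5 ≤ 168, that is T ≤ 163.5 − L. This limit is 163.5 h (6.8 days) at L = 0 and 151.5 h (6.3 days) at L = 12. Patients stopped before then have both wean and check inside the log.

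**6. On the anchor in 10.6.** Counting from administration removes L. The latest check is then 0.5 h late (wean inside) or 4.5 h late (wean after). Moving 8.3 to that anchor would shrink the gap but not close it.

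**7. Illustration for the stopping rule, on assumptions not in the documents.** Suppose the counted AE rate is 20%, a fraction f of EMR patients completes the course, and a fraction h of those has an uncounted qualifying event on stopping. The true rate is 1 − (1 − 0.20)(1 − f × h). With f = 0.25 and h = 0.05 it is 21%; with f = 0.75 and h = 0.20 it is 32%. The early-stop probability stays at 18%, against 21% to 70% if those events were counted. This shows how sensitive the rule would be if such events were left out; it is not an estimate for this trial.

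**The case against.** The strongest reply is that this is a gap of hours, in some patients only, with no loss of clinical detection. Much of that stands.

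- **A reader might infer that every completer has the end of the infusion and the whole wean unlogged.** The documents do not establish this. The wean may lie inside the seven days, and at zero lag it would then be wholly logged. If 7 days means calendar days, with recruitment as Day 0 (7.2), logging to the end of Day 7 would close 168 to 192 h after enrollment and would cover some stops. Section 8.3 does not say so.
- **A reader might take 16.5 h as the typical gap.** It is a ceiling. Referral, screening, permission and consent consume part of the same 12 hours, so a 12-hour lag would need enrollment at the instant that clock starts.
- **A reader might infer that hypoglycemia on stopping EMR is generally missed.** It is not. Section 9.0 lists many routes to earlier stopping, and those patients are generally weaned within the log. The purpose stated in 6.3 is attached to stopping for enteral feeding. The glucose cautions in 8.2 are attached to hypernatremia, suspected SIADH and anaphylaxis. None concerns completion at day 7.
- **A reader might infer that the stopping rule is biased by the enrollment lag.** Section 10.6 has its own anchor, so the lag enters only if the 8.3 log is its sole source, which is not stated. The rule also counts severe hyper/hypoglycemia, not every value below 70 mg/dL.

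What the reply does not remove: on elapsed time, the latest permitted check falls after closure under every combination in the table, and the two sections still use different anchors.

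**Conclusion.** The concern holds in a limited form and should be corrected. For patients who complete or nearly complete the course, the post-stop glucose check can fall after AE logging closes, and part or all of the wean may be unlogged too. A listed SAE on stopping a full course could then go unreported.

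The size depends on an elapsed-time reading of 8.3, on the assumed lag range, and on where the wean sits. The share of EMR patients affected is unknown: the ICU stay in 10.1 (mean 9.45, SD 13.06 days) does not give the fraction still on the infusion at day 7. Any effect on the 10.6 rule is smaller, at 0.5 to 4.5 h on its own anchor, unless the rule is fed only by the 8.3 log. This is a reporting gap. It does not touch the primary endpoint or bedside care.

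**What to change.** Define one AE/SAE window and use it in both 8.3 and 10.6. In the EMR arm, run it from randomization until the infusions and wean have fully stopped and the post-stop glucose check is done, for example plus 24 h. Keep the present 7 days as the minimum, so that patients stopped early lose no logging. Give the SC arm a matching fixed cut-off, for example day 8, so that the arms are compared over similar periods. With a 24-hour margin, full-course EMR logging would end between 168 + 24 = 192 h and 184 + 24 = 208 h after enrollment. The end of calendar Day 8, with recruitment as Day 0, falls 192 to 216 h after enrollment.

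State whether days are elapsed or calendar, and whether the 4-hour wean is part of the seven days; the documents leave both open. The 24-hour margin and day 8 are examples, and any choice that covers the check will serve.

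The cost is about one more day of AE logging per patient, in patients already followed for up to 90 days, plus aligned wording in two sections. No dosing, weaning or glucose rule changes, and the stopping boundaries can stand.
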